### 5.3.3 Patient Assessments

At 3, 12, 24, 60 and 120 months post-treatment, subjects will be asked to complete the following assessments:

- Oxford Shoulder Score
- EQ-5D-5L

This information will be transferred from a paper copy into the eCRF by the study site. These assessments will be completed by the subject, and may be completed at a clinic visit, or returned to the site by post, within the required assessment window.

## 5.4 Adverse event and Device Deficiency reporting

Pre-operatively, and at each follow-up assessment (immediate post-operative, 3, 12, 24, 60 and 120 months post-treatment), details of any device deficiency, adverse event or adverse device effect reported will be recorded in the eCRF. Details to be recorded include the nature, onset, duration, seriousness, relationship to the device and outcome of the event (see Section 6.3).

The occurrence of adverse events (including new illnesses, worsening symptoms of coexisting disease(s) or additional symptoms) will be identified by spontaneous reports from the subject in response to a standard question (e.g. how have you been since your last visit?) or by clinical/radiological assessment.

## 5.5 Radiographic Assessments

All radiographs will be submitted to an imaging vendor, Medical Metrics Inc. (MMI) for review and evaluation. MMI will complete eCRFs to document the radiographic findings under the scope of the study specific Radiographic Evaluation Protocol (Exhibit B).

## 5.6 Subject Discontinuation

Subjects are free to withdraw their consent to participate in the study at any time.

Subjects may be withdrawn by the investigator if they consider that the subject is unable to fulfil their requirements of participation.

Subjects may be documented as lost to follow up at the end of the study where they have not formally withdrawn their consent, but do not attend all required follow up visits/study schedule assessments on the request of the investigator.

A subject will be documented as withdrawn in the event of their death during the study.

The maximum recruitment limit at each site applies to subjects that successfully receive the study device.

In the instance of a consented subject withdrawing from the study pre-operatively or intra-operatively, they can be replaced by the investigator with another suitable subject.

## 6. RISK ANALYSIS

### 6.1 Study Related Risks

Any surgical procedure poses a potential risk and the procedures undertaken as part of this clinical investigation are no exception. There are known risks associated with the method of anaesthesia (general, epidural, local). In addition to these there are risks associated with a surgical procedure that involves a device. The risks that are associated with the study devices are similar to those of any total shoulder arthroplasty.

As specified in the Instructions For Use (IFU) (Exhibit C and included in the implant packaging), the following are generally the most frequently encountered adverse events and complications in total shoulder arthroplasty. Some of the identified risks are not directly applicable to this study, however any adverse events should be reported.

- Early or late loosening of the prosthetic components(s), often related to factors listed in **WARNINGS** and **PRECAUTIONS**.
- Change in position of the prosthesis, often related to factors listed in **WARNINGS** and **PRECAUTIONS**.
- Subluxation or dislocation of the replaced joint.

- Temporary inferior subluxation (this condition generally disappears as muscle tone is regained).
- Early or late infection.
- Hematoma and/or delayed wound healing.
- Cardiovascular disorders including venous thrombosis, pulmonary embolism and myocardial infarction.
- Pneumonia and/or atelectasis.
- Systemic or local adverse events or complications resulting from anaesthesia.

## 6.2 Study Participation Benefit Analysis

There are no potential benefits to study subjects from participation in this study. The knowledge gained from this investigation may help future shoulder arthroplasty patients.

## 6.3 Adverse Event Determination and Reporting

**Adverse Event Determination** will be done by the Principal Investigator or appropriate designee.

**An Adverse Event (AE)** is defined as an untoward medical occurrence, unintended disease or injury, or untoward clinical signs (or change or worsening of a pre-existing medical condition) in a patient, which may or may not have an association with the device.

**Adverse Device Effect (ADE)\*** is defined as an Adverse Event related to the use of an investigational medical device.

NOTE 1- This includes any adverse event resulting from insufficiencies or inadequacies in the instructions for use, the deployment, the implantation, the installation, the operation, or any malfunction of the investigational medical device.

NOTE 2- This includes any event that is a result of a use error or intentional misuse.

**Serious Adverse Device Effect (SADE)\*** is defined as an Adverse Device Effect that has resulted in any of the consequences characteristic of a serious adverse event.

**\*Per MEDDEV 2 12-1 rev.8 Vigilance - Section 3.1.4: Users should report INCIDENTS with MEDICAL DEVICES to the Manufacturer or the Competent Authority depending on national practice.**

**Serious Adverse Event (SAE)** is defined as an Adverse event that:

- a) led to a death,
- b) led to a serious deterioration in health that either:
  - 1) resulted in a life-threatening illness or injury, or
  - 2) resulted in a permanent impairment of a body structure or a body function, or
  - 3) required in-patient hospitalization or prolongation of existing hospitalization, or
  - 4) resulted in medical or surgical intervention to prevent life threatening illness or

injury or permanent impairment to a body structure or a body function.

c) led to fetal distress, fetal death or a congenital abnormality or birth defect.

NOTE 1: This includes device deficiencies that might have led to a serious adverse event if a) suitable action had not been taken or b) intervention had not been made or c) if circumstances had been less fortunate. These are handled under the SAE reporting system.

NOTE 2: A planned hospitalization for pre-existing condition, or a procedure required by the Clinical Investigation Plan, without a serious deterioration in health, is not considered to be a serious adverse event.

*Examples include allergic bronchospasm (a serious problem with breathing) requiring treatment in an emergency room, serious blood dyscrasias (blood disorders) or seizures/convulsions that do not result in hospitalization. The development of drug dependence or drug abuse would also be examples of important medical events.*

This protocol requires each site to report adverse events to the Sponsor according to the timelines below, record them in the subject's CRF, and inform their respective Ethics Committee (EC), per the Committee requirements.

#### Reporting Timelines

- **Serious Adverse Events (SAES)/Serious Adverse Device Effects (SADEs) and Unexpected Adverse Device Effects (UADES) - AS SOON AS POSSIBLE but no later than 72 hours after becoming aware**
- **Adverse vents (AEs) and Adverse Device effects (ADEs) AS SOON AS POSSIBLE but no later than 14 days after becoming aware**

**Determination of ADEs and SADEs:** The determination whether the AE is related to the device or procedure will be based upon whether a causal relationship between the device or procedure and the AE is at least a reasonable possibility, i.e. the relationship cannot be ruled out. A causal relationship cannot be ruled out if, in the medical judgment of the Investigator, the effect follows a reasonable temporal association with the use of the device and/or is confirmed by the improvement of the effect upon discontinuation of the clinical use of the device, and/or the effect is not reasonably explained by the Subject's clinical state.

#### Anticipated/Unanticipated Adverse Events (Expected/Unexpected)

The PI is responsible for determining whether an AE is **anticipated** or **unanticipated**. This determination is based on whether, in the opinion of the PI, the severity, type and frequency of the AE is consistent with the Instructions for Use (IFU). Please note that since TSA is a routine elective procedure, the vast majority of adverse events are anticipated and included in IFU.

When a PI classifies an AE as unanticipated, the Sponsor will also review and classify anticipated/unanticipated based on the reported event and in consideration of the IFU and internal risk reports. If the Sponsor has a different opinion on an anticipated/unanticipated classification a query will

be generated. When there is a discrepancy between the site and the Sponsor, both opinions will be recorded and reported as required to the relevant EC.

**Relationship to study device or procedure should be rated as follows:**

**none** (definitely not related): there is no relationship between study device or procedure and the event.  
**possible** (remote possibility, possibly, or probably related): the relationship between study device or procedure could exist if there is no contradicting evidence that can reasonably explain the Subject's condition.

**definite** (definitely related): the relationship between study device or procedure and event does exist and is confirmed upon further investigation by the Investigator.

Pre-existing medical conditions or symptoms reported prior to device implantation are not to be recorded as AEs. In the event there is an exacerbation of the pre-existing medical condition or symptoms, then an AE must be reported.

AEs are reported beginning from implantation/operative procedure until subject participation has ended (study completed or consent withdrawn). AEs must be followed to resolution, or until the study completion or consent withdrawal. When a subject ends participating in the trial (either study completion or consent withdrawal), an AE must be designated either as "resolved" (end date must be provided), or as "ongoing."

Subjects should be encouraged to report AEs spontaneously and may volunteer AE information at any time. At each evaluation, the Investigator will determine whether an AE has occurred. If it is determined that an AE has occurred and is reportable, the Investigator should obtain all the information required to complete the appropriate AE form eCRF. If an event occurs at an outside institution, the Investigator should attempt to obtain, if possible, required AE information.

The Investigator will record the nature, severity, treatment and outcome of the AE, and will determine their association to the device or the study procedure.

**The following categories of AE severity are to be used:**

**mild:** awareness of a sign, symptom or event that is easily tolerated and transient in nature with minimal or no impairment to normal activity.

**moderate:** moderate symptoms that are poorly tolerated, sustained, interfere with normal activity and require medical attention.

**severe:** symptom(s) require intervention, and the activities of daily living are significantly altered.

#### **6.4 Minimization of Risks**

The Sponsor will further minimise the identified and/or emergent risks throughout the study, by reviewing the reported adverse events and adverse effects. A Medical Monitor will be assigned to the project and complete a quarterly review of safety data to ensure no trends or signals are evident. Additionally, a Clinical Events Committee (CEC) comprised of an independent group of orthopaedic surgeons will meet prior to primary analyses to review and adjudicate AE data. Details about the CEC may be found within the associated charter.

Device related AEs will be reviewed and reported as per the required current regulatory requirements to the Notified Body. Based upon an evaluation of such events, the Sponsor may either amend the investigational plan or terminate the investigation to protect the rights, safety and welfare of the study subjects.

Should an EC decide to suspend or withdraw its approval for an Investigator to conduct the study at that institution, based on unacceptable risks to the study subjects, the study Sponsor will notify all reviewing ECs and Investigators of this action. To further minimise risks, any new information obtained during the course of the study relating to unanticipated adverse findings will be provided to all subjects, Investigators, and ECs.

The study has been designed to minimize the number of subjects yet provide sufficient numbers of subjects for valid scientific analysis of the compiled study data. The study design, the procedures for monitoring and the documentation, reporting and evaluation of the results from its surgical use will further control risks.

Only trained orthopaedic surgeons with expertise in treating this condition will conduct surgeries.

#### **6.5 Early Termination or Suspension**

The Sponsor, Ethics Committee or Regulatory Authority may prematurely terminate or suspend the clinical study as a whole or at an individual investigational site for significant and documented reasons. The Investigator may also prematurely terminate or suspend the clinical study at his/her site, for significant and documented reasons. Reasons for premature termination or suspension by any party include, but are not limited to safety, inadequate recruitment, Investigator issues, device related problems, alignment with business strategy or administrative issues.

If suspicion of an unacceptable risk to subjects arises during the clinical study, or when instructed by an Ethics Committee or Regulatory Authority, the Sponsor shall suspend the clinical study at all active sites while the risk is assessed. The Sponsor shall terminate the clinical study if an unacceptable risk is confirmed, or resume the clinical study following appropriate communication and approval from the Ethics Committee and Regulatory Authority as required.

In terminating the clinical study, the Sponsor and the Investigator will assure that adequate consideration is given to the protection of the subject's interests and all documentation is archived and the appropriate bodies such as the Ethics Committees and Regulatory Authorities are informed as appropriate.

## **7. STATISTICAL METHODOLOGY**

Statistical analysis will be performed using SAS® (SAS Institute Inc., [name]) software version 9.3 or higher. Any further software, such as MEDRA coding, that may be necessary will be described in the final study report.

### **7.1 Study Design**

This is a prospective, multicentre, uncontrolled, one-arm study. During this study, 157 subjects will be implanted with the device. Approximately 20 sites will be approved to participate in this study.

Patients will be clinically followed after surgery at immediate post-op, 3, 12, 24, 60 and 120 month visits. Data collected at the 24-month interval visit will be used in determining success on the primary endpoint.

### **7.2 Treatment Assignment**

The GLOBAL ICON stemless humeral component is the only device of interest in this study; there will be no control group.

### **7.3 Levels of Significance**

Unless otherwise stated, confidence intervals will be 2-sided 95% confidence intervals, and p-values below 0.05 will be deemed to be statistically significant. Unless otherwise stated, there will be no adjustment of significance levels because of testing multiple hypotheses.

### **7.4 Interval Windows**

The following scheduled visits as shown in Table 1, Section 1 have the following visit windows:

**Table 2: Interval Windows**

Analysis Visit	Study Visit	Study Interval (Days from Surgery)	Visit Window
Baseline	Pre-Op	--180 days to day of surgery (day 0)	-180 to 0 days
Surgery	Surgery	0	
Immediate Post-Op	Immediate Post-Op	0-10	5 (-5 to +5 days)
3 Months	3 Months	35 – 126	80 ± 45 days
12 Months	12 Months	281 - 449	365 ± 84 days
24 Months	24 Months	646 - 1644	730 - 84 days 730 + 914 days
60 Months	60 Months	1645 - 2005	1825 ± 180 days

120 Months	120 Months	3470 – 3830	3650 ± 180 days
------------	------------	-------------	-----------------

The intervals defined in the visit window column will be used to determine if data are collected within the protocol specified visit windows. Data collected at planned and unscheduled visits will be allocated according to the visit windows based on the collection date. The primary endpoint will use the data collected within the 24-month interval window. Secondary and tertiary endpoints will make use of the analysis visit, that is, the visit to which the data are mapped. If multiple records are allocated to the same analysis visit and one of the records is the planned collection, that record will be maintained for the primary, secondary and tertiary analyses. If none of the records are from planned collections, the record closest to the target study day for the visit will be used. Any planned visits conducted outside of the window will be considered a protocol deviation.

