### 5.3 Follow-Up Assessments

The Investigator will also inform the subject's local doctor / General Practitioner (GP) in writing of the subject's participation in this investigation at the same time as advising of the surgical procedure, providing the subject gives their consent to this process.

Subjects will be followed up as part of the clinical investigation at the following time points (date range for acceptable time window):

- Discharge/immediate post-operative (0-10 days)
- 3 months (35-126 days OR 5-18 weeks) post treatment
- 12 months (281-449 days OR 40-64 weeks) post treatment
- 24 months (646-1644 days OR 92-234 weeks) post treatment
- 60 months (1645-2005 days OR 235-286 weeks) post treatment
- 120 months (3470-3830 days OR 495-547 weeks) post treatment

All follow-up assessments and applicable unscheduled (*i.e.*, unplanned or unscheduled that occur between the protocol defined visit windows) visits will be recorded in the subject's eCRF by the Investigator study team unless otherwise indicated.

Both study and unscheduled office visits are defined as any visit at the study site where a study subject is seen by one of the site staff including the Principal Investigator (PI), any Sub-investigator (as appropriate), or anyone identified on the PI's team/delegation of authority.

An unscheduled visit is to be documented on an Unscheduled Visit eCRF/CRF when:

1. A subject returns for an additional visit during a study visit interval as described in **Table 1 - Time and Events**.
2. A subject returns between study visit intervals

If the previous protocol-defined study interval visit was missed, the required eCRFs/CRFs in the previously missed interval visit are also required to be completed along with the Unscheduled Visit eCRF.

If an unscheduled visit is related to a new, worsening, or resolved adverse event, both an AE eCRF and the Unscheduled Visit eCRF are to be completed.

**Important note:** Adverse Event (AE), including serious AEs, information is to be collected at ALL interactions with the study subject. This includes when non-site staff treats the study subject in a manner where the source documentation is available to the site staff. The site staff is responsible to review the medical event and report it per the protocol.

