### 7.6 Hypothesis Testing of Primary Endpoint

The primary endpoint analysis will seek to demonstrate that at 24 months after surgery, the composite success ( $p$ ), which is based on the absence of all four clinical outcomes (continuous RLL around the component, adjusted Constant-Murley Score  $\leq 85$ , component removal, SADE), is significantly greater than a performance goal of 75%. The null and alternative hypotheses for this endpoint are as follows:

Null hypothesis  $H_0: p \leq 75\%$

Alternative hypothesis  $H_A: p > 75\%$

**Decision Criterion:** The null hypothesis will be rejected and the alternative hypothesis will be concluded if the lower bound of a 2-sided 95% confidence interval is greater than 75%.

[figure not shown]

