1.4 Tertiary Objectives

Tertiary objectives are to evaluate levels of improvement, evaluated as a change from baseline for each post-operative assessment time point, for the adjusted Constant-Murley Score, Oxford Shoulder Score and EQ-5D-5L. This will be evaluated by examining change from baseline at 3-, 12-, 24-, 60-, and 120- month visits. Lastly, survival of the GLOBAL ICON stemless humeral component for the reason of periprosthetic fracture will be reported using Kaplan-Meier methodology. Survival will be reported on the last day of the 24-, 60- and 120-month assessment windows.

2. Treatment Assignment

Treatment assignment is described in Section 1.

3. Randomization and Blinding

Neither randomization nor blinding will be implemented in this study.

4. Interval Windows

Data collected throughout the study will be assessed for compliance with the protocol-specified visit schedule.

Table Seven windows are defined based on the number of days prior to or after surgery (Day 0): baseline, Immediate post-op, 3-months post-op, 12-months post-op, 24-months post-op, 60-months post-op and 120-months post-op. If multiple visits fall into the same interval, the result latest in the visit window with complete data will be used in the analysis.

Table 1. Interval Windows

Analysis Visit	Study Visit	Study Interval (Days from Surgery)	Visit Window
Baseline	Pre-Op	-180 days to day of surgery (day 0)	-180 to 0 days
Surgery	Surgery	0	
Immediate Post-Op	Immediate Post-Op	0-10	5 (-5 to +5 days)
3 Months	3 Months	35 – 126	80 ± 45 days
12 Months	12 Months	281 – 449	365 ± 84 days
24 Months	24 Months	646 - 1644	730 - 84 days 730 + 914 days
60 Months	60 Months	1645 - 2005	1825 ± 180 days
120 Months	120 Months	3470 – 3830	3650 ± 180 days

5. Description of Scales and Scoring

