9.4 Hypothesis Testing of Primary Endpoint

The primary endpoint analysis will seek to demonstrate that at the 24 month visit after surgery, the composite success (p), which is based on four study outcomes (radiograph demonstrating no continuous radiolucent line around the humeral component, adjusted Constant-Murley Score > 85, no removal of the humeral component, no serious adverse events related to the device), is significantly greater than a performance goal (PG) of 75%. The null and alternative hypotheses for this endpoint are as follows:

Null hypothesis H_{01} : $p \leq 75\%$

Alternative hypothesis H_{A1} : $p > 75\%$

The null hypothesis will be rejected and the alternative hypothesis will be accepted if the lower bound of a two-sided 95% confidence interval is greater than 75%. The performance goal of 75% used in the hypothesis test described above is based on the percentage of successful stemmed implants at the 24 month visit reported elsewhere using a similar definition of success [4]. Therefore, the hypothesis test implies a comparison to performance of stemmed implants. In a prior study, non-inferiority of the Simpliciti stemless humeral device to stemmed devices was demonstrated using a PG of 65% (75%-10% non-inferiority margin) [4]. Therefore, the current study sets a higher bar to establish successful performance of Global Icon when compared to the study evaluating the Simpliciti device.

Another objective using the same endpoint is to establish non-inferiority of Global Icon to Simpliciti conditional on rejection of H_{01} . To do so a PG or non-inferiority margin of 78.74% (Simpliciti success percentage of 88.74% [5] -10%) is selected. The null and alternative hypotheses for this objective are as follows:

Null hypothesis H_{02} : $p \leq 78.74\%$

Alternative hypothesis H_{A2} : $p > 78.74\%$

The null hypothesis will be rejected and the alternative hypothesis will be accepted if the lower bound of a two-sided 95% confidence interval is greater than 78.74%. Notably,

simultaneous testing of these nested null hypotheses (H_{01}, H_{02}) does not inflate the Type I error rate [6,7].

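### The 24-month primary endpoint accepts assessments up to day 1644, the protocol and SAP pick different records within that window, and no planned analysis shows the composite near day 730

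*Protocol*

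**What the plan says.** **Window.** Protocol 5.3 lists the visit as "24 months (646-1644 days OR 92-234 weeks) post treatment". Protocol Table 1, Protocol Table 2 and SAP Table 1 give the same limits; the two interval tables write them as "730 - 84 days 730 + 914 days". Protocol 7.4 adds: "The primary endpoint will use the data collected within the 24-month interval window".

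**Time point of the claim.** Protocol 7.6 begins: "The primary endpoint analysis will seek to demonstrate that at 24 months after surgery". It then asks whether composite success is "significantly greater than a performance goal of 75" per cent. The sample size (Protocol 7.8, SAP 8) assumes 85% success at 24 months. SAP 9.4 says the 75% goal is "based on the percentage of successful stemmed implants at the 24 month visit reported elsewhere".

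**Choice of record.** Under Protocol 7.4, a planned record takes precedence over others in the same window. Failing that, "If none of the records are from planned collections, the record closest to the target study day for the visit will be used". SAP section 4 has a different rule for several visits in one interval: "the result latest in the visit window with complete data will be used in the analysis".

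**Other analyses.** The sensitivity analyses of the primary endpoint are the beta-binomial site model (SAP 9.5.2) and the Per Protocol repeat (SAP 9.9). SAP 1.2 reports Kaplan-Meier survivorship for 24 months at the last day of the assessment window.

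**The concern.** Two subjects, one assessed at 21 months and one at 54 months, both count as 24-month outcomes. Component removal and device-related serious adverse events accumulate, so a subject assessed late has had longer to fail. The Constant-Murley score and the radiographs also come from a different stage of recovery or wear. The estimate then blends time points in proportions set by when subjects attend and by which record rule is applied, while the test sets it against a 24-month figure.

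The record rules add to this. Under the SAP rule, a subject with a complete visit on day 730 and another complete visit on, say, day 1500 is scored on day 1500. A Constant-Murley score of 84 at the first and 86 at the second would turn a failure on that criterion into a pass, and the reverse is equally possible. Under the protocol rule, the planned visit would be kept. The two documents can therefore give different primary results from the same data.

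Protocol 7.10 plans to use the primary analysis in a US marketing application. It matters there whether the reported rate can be read as a 24-month rate.

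**Working it through.** **1. Width of the window** (Protocol Table 2; 30.4375 days per month)
- Start: 730 - 84 = 646; 646 / 30.4375 = 21.2 months.
- End: 730 + 914 = 1644; 1644 / 30.4375 = 54.0 months. The 60-month window opens on day 1645.
- Width: 1644 - 646 = 998 days. The 12-month window is 449 - 281 = 168 days, so the ratio is 998 / 168 = 5.9.
- Share after day 730: 914 / 998 = 92%.
- A window shaped like the 12-month one (730 ± 84) would end on day 814. Share of the present window after that: (1644 - 814) / 998 = 83%.

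**2. The plan's own sample size.** Exact binomial test, 75% against 85%, one-sided 0.025: at n = 133 the critical count is 110, with attained alpha 0.0223 and power 80.8%. Allowing for attrition, 133 / 0.85 = 156.5, rounded up to 157. Both stated figures reproduce. The sample size is not in question here.

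**3. Does any planned analysis isolate 24 months?**
- SAP 9.5.2 models variation between sites, not timing.
- SAP 9.9 uses the Per Protocol set. A day-1600 visit is in window, so its timing alone is not a deviation and does not exclude the subject.
- Kaplan-Meier survivorship covers removal only, and its 24-month value is read at day 1644.
- The 24-month secondary and tertiary scores use the same window.
- SAP 9.8.5 would impute radiolucency, device-related serious events and revision irrespective of their timing.

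**4. Illustrated drift.** Neither document gives a failure rate after 24 months or the share assessed late. Both are assumed here.
- Loss of success between day 730 and day 1644 = 0.85 × (1 - exp(-rate × 914 / 365.25)), where 914 / 365.25 = 2.50 years.
  - 0.5% per year: 0.85 × 0.0124 = 1.1 points.
  - 3% per year: 0.85 × 0.0723 = 6.1 points.
- Pooled shift = share assessed after day 814 × 0.85 × mean loss, with late assessments spread evenly over days 814-1644 and loss counted from day 730.
  - 10% late, 1% per year: 0.10 × 0.85 × 0.0135 = 0.1 points.
  - 30% late, 3% per year: 0.30 × 0.85 × 0.0400 = 1.0 point.

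**5. Drift in either direction.** Take n = 133 and the planned rule (lower Wald 95% bound above 75%), which needs at least 109 successes. Ignore imputation. Assume 20% of subjects are assessed late and that their success rate differs from the 24-month rate by the amount shown.

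| Late minus 24-month success | P(goal met), true 24-month success 75% | P(goal met), true 24-month success 85% |
|---|---|---|
| -10 points | 1.1% | 67.6% |
| -5 points | 2.0% | 78.0% |
| 0 | 3.6% | 86.4% |
| +5 points | 6.3% | 92.5% |
| +10 points | 10.3% | 96.4% |

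Each entry is a binomial tail at the blended rate; for example, 0.75 + 0.20 × 0.10 = 0.77.

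**The case against.** A wide window keeps observed outcomes that would otherwise have to be imputed, and that is a sound reason to use it for the primary analysis. This stands; narrowing the primary window is not proposed.

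Timing is not wholly hidden. Removals get a Kaplan-Meier analysis, and adverse events are tabulated by period of onset and listed (Protocol 7.9.2, SAP 9.6). This also stands, and it limits the gap to the composite, the Constant-Murley score and the radiographic result. The table shells are a separate document that was not available, so the absence applies to the protocol and SAP text.

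The illustrated pooled shift of 0.1-1.0 points is small beside a Wald half-width of about 5.6 points (1.96 × √(0.85 × 0.15 / 157)) and the 10-point gap between 75% and 85%. Extra time to fail makes the goal harder to meet, not easier. Both remarks are fair for removals and device-related events. They do not settle the Constant-Murley criterion, which may improve or decline after 24 months.

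The protocol's closest-to-target rule is a partial safeguard. It operates only when a window holds several records and none is planned, it does not help when the planned visit itself is late, and the SAP rule contradicts it.

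A reader might infer that the comparison with the goal is invalid, or that the window favours the device. The documents support neither. They do not give the visit windows of the studies behind the 75% and 88.74% figures, the number of subjects assessed late, or the direction of any change.

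**Conclusion.** The point holds as a mismatch between the time the claim names and the time the data may represent, made worse by two conflicting record rules. The estimate may not be like-for-like with the 24-month goal, and the planned outputs would not let a reader judge how far late assessments affect the composite.

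The size is unknown. Under the assumed rates, accruing failures lower success by about 1.1-6.1 points between day 730 and day 1644, and lower the pooled estimate by about 0.1-1.0 points. A change in Constant-Murley score could add to that or reverse it. The primary test is not shown to be invalid and the sample size is not in error. A pre-specified check is worth having because it is cheap and would show whether the conclusion holds at 24 months.

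**What to change.** Keep days 646-1644 for the primary analysis and make three changes.

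1. **Record rule.** Replace the latest-complete rule in SAP section 4 with the rule in Protocol 7.4: the planned record, otherwise the one closest to day 730.
2. **Sensitivity analysis.** Add to SAP 9.9 a repeat of the primary analysis that uses only assessments in days 646-814. Treat later values as missing at 24 months, but keep them as auxiliary variables in the imputation model. Count removals and device-related serious adverse events for every subject through one fixed day, for example day 814.
3. **Reporting.** Give the distribution of assessment days, including the number after day 814, and Kaplan-Meier survivorship at day 730 as well as at day 1644.

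The cost is a short SAP amendment and one extra analysis run, which will carry more imputed outcomes and so be less precise than the primary. No visit or data collection changes.
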